6.12.1.4 Echocardiogram

Absolute values and change from baseline in LVEF will be summarized by visit as per Section 5.1.2. Additionally, shift tables based on the NCI-CTCAE Version 5.0 toxicity grading scale will be presented for LVEF between pre-treatment and worst case on-treatment.

6.12.1.5 Vital Signs

Absolute value and change from baseline for all vital signs parameters as listed in Section 4.2.5 will be summarized by visit. Continuous variables will be summarized by the number of participants, mean, SD, median, minimum, and maximum values. Categorical variables will be summarized by absolute counts (n) and percentages (%). Percentages will be based on the number of participants with data.

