2.3. Benefit/Risk Assessment

To date, the safety profile of single-agent mirdametinib (PD-0325901) in patients with advanced cancer (doses < 10 mg BID, intermittent schedule) has been characterized by mostly manageable and reversible toxicities. The most frequently reported adverse events have been rash, nausea, vomiting, diarrhea, and fatigue. The majority of the events were mild-to-moderate intensity. Other events that have been reported in lesser frequency include ocular disorders (visual disturbances, blurred vision, retinal vein occlusion), nervous system disorders (including confusion, slowed ideation, slurred speech, and hallucinations), musculoskeletal and connective tissue disorders (general weakness as well as neck muscle weakness associated with mild and moderate elevations in creatine kinase [CK]), and cardiac disorders (decreased left ventricular ejection fraction [LVEF], congestive heart failure). These events primarily occurred in patients receiving doses ≥ 10 mg (up to 30 mg) BID.

In order to minimize potential risk during study participation, participants will be carefully monitored for the development of toxicities throughout the study and guidelines for dose modification/discontinuation for selected adverse events are provided.

Based on the available nonclinical and clinical trial data, the benefit-risk balance is considered favorable for further development in patients with NF.

More detailed information about the known and expected benefits and risks and reasonably expected adverse events of mirdametinib (PD-0325901) may be found in the Investigator's Brochure.

3. Objectives and Endpoints

Table 1 Study Objectives and Endpoints

Objectives	Endpoints
Primary	
To evaluate the confirmed complete and partial response (PR) rate of mirdametinib (PD-0325901) using volumetric magnetic resonance imaging (MRI) analysis in participants with an inoperable NF1-associated PN that is causing significant morbidity.	Objective response rate at the end of the Treatment Phase (defined as PN decrease ≥ 20% compared to Baseline) using centrally read MRI volumetric analysis.
Secondary	
To evaluate the safety and tolerability of mirdametinib (PD-0325901) in participants with NF1 and symptomatic inoperable PN as measured by the incidence of adverse events (AEs);	Safety endpoints will include incidence of treatment-emergent adverse events, changes in laboratory parameters, vital signs, physical examination findings, and electrocardiograms (ECGs);

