- 10. Participant has experienced any of the following within 6 months (24 weeks) of signing informed consent/assent: clinically significant cardiac disease, myocardial infarction, severe/unstable angina, coronary/peripheral artery bypass graft, cerebrovascular accident, transient ischemic attack, or symptomatic pulmonary embolism;
- 11. Participant has recorded a LVEF < 55% at Screening or within 3 years of signing informed consent/assent, OR has a history of congestive heart failure;
- 12. Participant has a history of, or evidence of, retinal pathology on ophthalmologic examination that is considered a risk factor for central serous retinopathy, retinal vein occlusion (RVO), or neovascular macular degeneration. Participants will be excluded from study participation if they have any of the following risk factors for RVO at Screening:

- 12.1. Intraocular pressure > 21 mmHg;
- 12.2. Serum cholesterol > 300 mg/dL;
- 12.3. Serum triglycerides > 300 mg/dL;
- 12.4. Hyperglycemia (fasting blood glucose > 125 mg/dL or random blood glucose > 200 mg/dL);
- 12.5. Age specific hypertension
 - 12.5.1. Participants \geq 13 years of age with a blood pressure \geq 140/90 mm Hg
 - 12.5.2. Participants \leq 12 years of age with a blood pressure \geq 95th percentile for age +12 mmHg (Section 10.11);
- 13. Participant has a history of glaucoma;
- 14. Participant has a history of a positive human immunodeficiency virus (HIV) antibody test;
- 15. Participant has a known malabsorption syndrome or preexisting gastrointestinal conditions that may impair absorption of PD-0325901 (e.g., gastric bypass, lap band, or other gastric procedures). Delivery of PD-0325901 via nasogastric tube or gastrostomy tube is not allowed;

Prior/Concomitant Therapy

- 16. Participant has received NF1 PN-targeted therapy (e.g., farnesyltransferase inhibitors, kinase inhibitors, etc.) within 45 days of first dose of study treatment (or 5.5 half-lives, whichever is longer). All toxicities from prior therapy must resolve to ≤ Grade 1 or Baseline;
- 17. Participant previously received or is currently receiving therapy with PD-0325901 or any other MEK1/2 inhibitor (e.g., selumetinib, trametinib, cobimetinib, binimetinib, etc.);

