10.3.1. Definition of AE

AE Definition

- An AE is any untoward medical occurrence in a patient or clinical study participant, temporally associated with the use of study treatment, whether or not considered related to the study treatment.
- NOTE: An AE can therefore be any unfavorable and unintended sign (including an abnormal laboratory finding), symptom, or disease (new or exacerbated) temporally associated with the use of study treatment.

Events Meeting the AE Definition

- Any abnormal laboratory test results (hematology, clinical chemistry, or urinalysis) or
 other safety assessments (e.g., ECG, radiological scans, vital signs measurements),
 including those that worsen from Baseline, considered clinically significant in the
 medical and scientific judgment of the Investigator (i.e., not related to progression of
 underlying disease).
- Exacerbation of a chronic or intermittent pre-existing condition including either an increase in frequency and/or intensity of the condition.
- New conditions detected or diagnosed after study treatment administration even though it may have been present before the start of the study.
- Signs, symptoms, or the clinical sequelae of a suspected drug-drug interaction.
- Signs, symptoms, or the clinical sequelae of a suspected overdose of either study treatment or a concomitant medication. Overdose per se will not be reported as an AE/SAE unless it is an intentional overdose taken with possible suicidal/self-harming intent. Such overdoses should be reported regardless of sequelae.
- "Lack of efficacy" or "failure of expected pharmacological action" per se will not be reported as an AE or SAE. Such instances will be captured in the efficacy assessments. However, the signs, symptoms, and/or clinical sequelae resulting from lack of efficacy will be reported as AE or SAE if they fulfil the definition of an AE or SAE.

Events NOT Meeting the AE Definition

- Any clinically significant abnormal laboratory findings or other abnormal safety
 assessments which are associated with the underlying disease, unless judged by the
 Investigator to be more severe than expected for the participant's condition.
- The disease/disorder being studied or expected progression, signs, or symptoms of the disease/disorder being studied, unless more severe than expected for the participant's condition.

- Medical or surgical procedure (e.g., endoscopy, appendectomy): the condition that leads to the procedure is the AE.

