10.11. Appendix 11: Pediatric Blood Pressure Charts

Table 12 Blood Pressure for Girls Aged 2 to 12 Years of Age

Age (y)	BP Percentile	SBP (mm Hg)								DBP (mm Hg)							
	Height (cm)	84.9	86.3	88.6	91.1	93.7	96	97.4	84.9	86.3	88.6	91.1	93.7	96	97.4		
2	95th	104	105	106	106	107	108	109	62	63	63	64	65	66	66		
	95th + 12 mm Hg	116	117	118	118	119	120	121	74	75	75	76	77	78	78		
	Height (cm)	91	92.4	94.9	97.6	100.5	103.1	104.6	91	92.4	94.9	97.6	100.5	103.1	104.6		
3	95th	106	106	107	108	109	110	110	64	65	65	66	67	68	69		
	95th + 12 mm Hg	118	118	119	120	121	122	122	76	77	77	78	79	80	81		
	Height (cm)	97.2	98.8	101.4	104.5	107.6	110.5	112.2	97.2	98.8	101.4	104.5	107.6	110.5	112.2		
4	95th	107	108	109	109	110	111	112	66	67	68	69	70	70	71		
	95th + 12 mm Hg	119	120	121	121	122	123	124	78	79	80	81	82	82	83		
	Height (cm)	103.6	105.3	108.2	111.5	114.9	118.1	120	103.6	105.3	108.2	111.5	114.9	118.1	120		
5	95th	108	109	109	110	111	112	113	68	69	70	71	72	73	73		
	95th + 12 mm Hg	120	121	121	122	123	124	125	80	81	82	83	84	85	85		
	Height (cm)	110	111.8	114.9	118.4	122.1	125.6	127.7	110	111.8	114.9	118.4	122.1	125.6	127.7		
6	95th	109	109	110	111	112	113	114	70	71	72	72	73	74	74		
	95th + 12 mm Hg	121	121	122	123	124	125	126	82	83	84	84	85	86	86		
	Height (cm)	115.9	117.8	121.1	124.9	128.8	132.5	134.7	115.9	117.8	121.1	124.9	128.8	132.5	134.7		
7	95th	109	110	111	112	113	114	115	72	72	73	73	74	74	75		
	95th + 12 mm Hg	121	122	123	124	125	126	127	84	84	85	85	86	86	87		
	Height (cm)	121	123	126.5	130.6	134.7	138.5	140.9	121	123	126.5	130.6	134.7	138.5	140.9		
8	95th	110	111	112	113	115	116	117	72	73	74	74	75	75	75		
	95th + 12 mm Hg	122	123	124	125	127	128	129	84	85	86	86	87	87	87		
	Height (cm)	125.3	127.6	131.3	135.6	140.1	144.1	146.6	125.3	127.6	131.3	135.6	140.1	144.1	146.6		
9	95th	112	112	113	114	116	117	118	74	74	75	75	75	75	75		
	95th + 12 mm Hg	124	124	125	126	128	129	130	86	86	87	87	87	87	87		
	Height (cm)	129.7	132.2	136.3	141	145.8	150.2	152.8	129.7	132.2	136.3	141	145.8	150.2	152.8		
10	95th	113	114	114	116	117	119	120	75	75	76	76	76	76	76		
	95th + 12 mm Hg	125	126	126	128	129	131	132	87	87	88	88	88	88	88		
	Height (cm)	135.6	138.3	142.8	147.8	152.8	157.3	160	135.6	138.3	142.8	147.8	152.8	157.3	160		
11	95th	115	116	117	118	120	123	124	76	77	77	77	77	77	77		
	95th + 12 mm Hg	127	128	129	130	132	135	136	88	89	89	89	89	89	89		
	Height (cm)	142.8	145.5	149.9	154.8	159.6	163.8	166.4	142.8	145.5	149.9	154.8	159.6	163.8	166.4		

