12	95th	118	119	120	122	124	125	126	78	78	78	78	79	79	79		
	95th + 12 mm Hg		131	132	134	136	137	138	90	90	90	90	91	91	91		

BP = blood pressure; cm = centimeter; DBP = diastolic blood pressure; SBP = systolic blood pressure; y = years

CONFIDENTIAL Protocol MEK-NF-201

Amendment 4 (17May2022)

Table 13 Blood Pressure for Boys Aged 2 to 12 Years of Age

Ago (v)	BP Percentile	SBP (mm Hg)								DBP (mm Hg)							
Age (y)		86.1 87.4 89.6 92.1 94.7 97.1 98.5								07.4			 	07.1	00.5		
	Height (cm)								86.1	87.4	89.6	92.1	94.7	97.1	98.5		
2	95th	104	105	105	106	107	107	108	57	58	58	59	60	61	61		
	95th + 12 mm Hg	116	117	117	118	119	119	120	69	70	70	71	72	73	73		
	Height (cm)	92.5	93.9	96.3	99	101.8	104.3	105.8	92.5	93.9	96.3	99	101.8	104.3	105.8		
3	95th	106	106	107	107	108	109	109	60	61	61	62	63	64	64		
	95th + 12 mm Hg	118	118	119	119	120	121	121	72	73	73	74	75	76	76		
	Height (cm)	98.5	100.2	102.9	105.9	108.9	111.5	113.2	98.5	100.2	102.9	105.9	108.9	111.5	113.2		
4	95th	107	107	108	108	109	110	110	63	64	65	66	67	67	68		
	95th + 12 mm Hg	119	119	120	120	121	122	122	75	76	77	78	79	79	80		
	Height (cm)	104.4	106.2	109.1	112.4	115.7	118.6	120.3	104.4	106.2	109.1	112.4	115.7	118.6	120.3		
5	95th	107	108	109	109	110	111	112	66	67	68	69	70	70	71		
	95th + 12 mm Hg	119	120	121	121	122	123	124	78	79	80	81	82	82	83		
	Height (cm)	110.3	112.2	115.3	118.9	122.4	125.6	127.5	110.3	112.2	115.3	118.9	122.4	125.6	127.5		
6	95th	108	109	110	111	112	113	114	69	70	70	71	72	72	73		
	95th + 12 mm Hg	120	121	122	123	124	125	126	81	82	82	83	84	84	85		
	Height (cm)	116.1	118	121.4	125.1	128.9	132.4	134.5	116.1	118	121.4	125.1	128.9	132.4	134.5		
7	95th	110	110	111	112	114	115	116	71	71	72	73	73	74	74		
	95th + 12 mm Hg	122	122	123	124	126	127	128	83	83	84	85	85	86	86		
	Height (cm)	121.4	123.5	127	131	135.1	138.8	141	121.4	123.5	127	131	135.1	138.8	141		
8	95th	111	112	112	114	115	116	117	72	73	73	74	75	75	75		
	95th + 12 mm Hg	123	124	124	126	127	128	129	84	85	85	86	87	87	87		
	Height (cm)	126	128.3	132.1	136.3	140.7	144.7	147.1	126	128.3	132.1	136.3	140.7	144.7	147.1		
9	95th	112	112	113	115	116	118	119	74	74	75	76	76	77	77		
	95th + 12 mm Hg	124	124	125	127	128	130	131	86	86	87	88	88	89	89		
	Height (cm)	130.2	132.7	136.7	141.3	145.9	150.1	152.7	130.2	132.7	136.7	141.3	145.9	150.1	152.7		
10	95th	112	113	114	116	118	120	121	76	76	77	77	78	78	78		
	95th + 12 mm Hg	124	125	126	128	130	132	133	88	88	89	89	90	90	90		

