Participants who complete Cycle 24 of the Treatment Phase and did not meet withdrawal criteria detailed in the protocol are eligible to participate in the LTFU Phase. Eligible participants will continue taking the last dose assigned in the Treatment Phase (approximately 2 mg/m² BID [maximum dose of 4 mg BID]) of mirdametinib, on an intermittent (3 weeks on/1 week off) dosing schedule in 28-day cycles. Participants will remain in the LTFU Phase until a withdrawal criterion is met as described in Section 7 of the protocol or mirdametinib is commercially available.

A participant is considered to have completed the Treatment Phase if he/she has completed the Cycle 24 visit (End of Treatment Phase) or has entered the LTFU Phase.

The treatment group labels that will be used in all outputs are presented in Table 2.

Table 2: Study Treatments

Actual Treatment	Treatment Label
PD-0325901 (approximately 2 mg/m ² BID)	Mirdametinib

Table 3 and Table 4 present the visit labels that will be used in all outputs for the Treatment and LTFU Phases, respectively.

Table 3: Study Visits – Treatment Phase

Visit	Visit Label
Screening	Screening
Cycle 1 – Week 1 (Baseline, study visit day 1)	C1D1
Cycle 1 - Week 3 (Cycle Day 15)	C1D15
Cycle 2 – Week 7 (Cycle Day 15)	C2D15
Cycle 3 – Week 11 (Cycle Day 15)	C3D15
Cycle 4 - Week 15 (Cycle Day 15)	C4D15
Cycle 5 – Week 19 (Cycle Day 15)	C5D15
Cycle 6 – Week 23 (Cycle Day 15)	C6D15
Cycle 7 - Week 27 (Cycle Day 15)	C7D15
Cycle 9 – Week 35 (Cycle Day 15)	C9D15
Cycle 11 – Week 43 (Cycle Day 15)	C11D15
Cycle 13 - Week 51 (Cycle Day 15)	C13D15
Cycle 15 – Week 59 (Cycle Day 15)	C15D15
Cycle 17 – Week 67 (Cycle Day 15)	C17D15
Cycle 19 – Week 75 (Cycle Day 15)	C19D15
Cycle 21 – Week 83 (Cycle Day 15)	C21D15
Cycle 23 – Week 91 (Cycle Day 15)	C23D15
Cycle 24 (End of Treatment Phase) - Week 96 (Cycle Day 21)	C24D21
Early Termination	ET
Safety Follow-up – 30 days after last dose	SFU

Document: S:\Q_146\Q_03974\MEK-NF-201\Prog_Stat\Documentation\SAP\MEK-NF-201 SAP v1.0.0.docx

Author:

Table 4: Study Visits - Long-Term Follow-up Phase

Visit	Visit Label
Cycle 28 (Cycle Day 15)	C28D15
Cycle 32 (Cycle Day 15)	C32D15
Cycle 36 (Cycle Day 15)	C36D15
Cycle XX (Cycle Day 15)	CXXD151
End of Treatment	EOT
Safety Follow-up = 30 days after last dose	LTSFU

¹The Long-Term Follow-up phase lasts an indefinite amount of time; visits will occur on day 15 of every 4th cycle with the cycle number inserted into this visit label format.

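### In the pooled 2 to 17 cohort, blood pressure is summarized only as raw mmHg value and change, so the mean change in this single-arm study includes growth

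*SAP*

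**What the plan says.** Protocol Section 3, Table 1, makes vital signs part of a secondary safety endpoint: "changes in laboratory parameters, vital signs, physical examination findings, and electrocardiograms (ECGs".

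The SAP implements this in three places:
- Section 4.2.5 lists systolic and diastolic pressure in mmHg, defines change as the post-baseline value minus baseline, and derives only body surface area.
- Section 6.12.1.5 then states: "Absolute value and change from baseline for all vital signs parameters as listed in Section 4.2.5 will be summarized by visit". Its general sentence on categorical variables has no blood pressure category to act on.
- Section 5.1.2 makes age cohort the default grouping, and the pediatric cohort is ages 2 to 17.

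The protocol holds a growth reference in Appendix 11 (Section 10.11): "Table 12 Blood Pressure for Girls Aged 2 to 12 Years of Age" and "Table 13 Blood Pressure for Boys Aged 2 to 12 Years of Age". Each gives the 95th percentile, and that value plus 12 mmHg, by age, sex and seven heights. The only use made of the charts is Exclusion 12.5, which is among "any of the following risk factors for RVO at Screening" (RVO is retinal vein occlusion). Up to age 12 the limit is the "95th percentile for age +12 mmHg (Section 10.11"; from age 13 it is 140/90.

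**The concern.** In growing children blood pressure rises with age and height without any drug effect. An uncontrolled mean change therefore adds growth to whatever the drug does, and the planned table cannot separate the two. A reader could take growth for a drug effect, or dismiss a real effect as growth.

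The absolute-value rows have a related weakness. They average children for whom the same reading means different things, because the level the protocol treats as too high at entry depends on age, sex and height. No planned table shows how many treated children later reach the level that would have excluded them at Screening.

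What is at stake is how one descriptive safety table can be read. The primary endpoint is not involved.

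**Working it through.** The documents state no expected blood pressure change, so there is no plan figure to reproduce. The check is how far the protocol's own charts move over the Treatment Phase.

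**Inputs.** Tables 12 and 13, 95th percentile, middle height column, ages 2, 3, …, 12:

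| Series | Values (mmHg) |
|---|---|
| Girls systolic | 106, 108, 109, 110, 111, 112, 113, 114, 116, 118, 122 |
| Boys systolic | 106, 107, 108, 109, 111, 112, 114, 115, 116, 118, 121 |
| Girls diastolic | 64, 66, 69, 71, 72, 73, 74, 75, 76, 77, 78 |
| Boys diastolic | 59, 62, 66, 69, 71, 73, 74, 76, 77, 78, 78 |

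The Cycle 24 visit is Study Day 665 (SAP Table 12).

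**Step 1. Two-year drift.** For entry ages a = 2 to 10, take the value at a + 2 minus the value at a. This assumes the child stays in the same height column and on the same percentile, and that this percentile moves as the 95th does.

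**Step 2. Scale to Day 665.** The factor is (664 / 365.25) / 2 = 0.909.

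| Series | Two-year differences | Mean | × 0.909 |
|---|---|---|---|
| Girls systolic | 3, 2, 2, 2, 2, 2, 3, 4, 6 | 26/9 = 2.89 | 2.6 |
| Boys systolic | 2, 2, 3, 3, 3, 3, 2, 3, 5 | 26/9 = 2.89 | 2.6 |
| Girls diastolic | 5, 5, 3, 2, 2, 2, 2, 2, 2 | 25/9 = 2.78 | 2.5 |
| Boys diastolic | 7, 7, 5, 4, 3, 3, 3, 2, 1 | 35/9 = 3.89 | 3.5 |

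**Step 3. Sensitivity to height.** Repeating this in all seven height columns gives systolic drift of 2.3 to 3.1 (girls) and 2.0 to 3.5 (boys), and diastolic drift of 2.1 to 2.8 (girls) and 3.2 to 3.8 (boys).

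**Step 4. Long-term follow-up.** SAP Table 4 includes "Cycle 36 (Cycle Day 15"). That is Day (36 − 1) × 28 + 15 = 995, or 994 / 365.25 = 2.72 years. Linear interpolation in the middle column, entry ages 2 to 9 (the chart ends at 12), gives systolic +3.7 (girls) and +3.8 (boys), and diastolic +3.7 and +5.3. The drift grows with follow-up.

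**Step 5. Spread of the entry limits.** A boy of 2 in the shortest column has an Exclusion 12.5 limit of 116/69. From age 13 the limit is 140/90. The gap is 140 − 116 = 24 systolic and 90 − 69 = 21 diastolic.

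**Step 6. Effect of referencing.** Under the Step 1 assumptions, a child who keeps the same distance from the chart line has a change of 0 when pressure is expressed as the difference from the tabulated 95th percentile. The same child shows the drift above on the raw scale.

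**The case against.** The strongest reply is that the plan does what it promised. Table 1 of the protocol asks for changes in vital signs, and the SAP delivers them in a table with no test or threshold to distort. Hypertension is not among the drug's risks in Protocol Section 2.3, is not an event of special interest, and has no dose-modification rule. This stands, and it keeps the point a minor one.

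There is also partial capture:
- A vital-sign finding that the investigator judges clinically significant is an adverse event (Protocol 10.3.1) and is tabulated.
- The maximum of within-child change would reveal a large rise in one child.
- Height and weight are summarized by visit in the same section, so a reader can see that the cohort is growing.
- The data monitoring committee reviews aggregate safety.

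None of these takes growth out of the mean change or counts children who reach an age-specific limit.

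A reader might infer four stronger things, which the documents do not support:
- **That the SAP is inconsistent with its own handling of QTcF and ejection fraction.** Those have on-treatment action limits in the protocol; blood pressure has none.
- **That the drift matches or exceeds the sampling error of the mean.** No standard deviation for blood pressure is given, so that rests on an assumed one.
- **That the drift is a large share of the 12 mmHg added to the 95th percentile.** That margin is an eligibility allowance for one child and is not a scale for a mean change.
- **That the larger diastolic shifts in the youngest boys would show in the results.** No planned table isolates that group, and for boys entering at 9 and 10 the two-year diastolic difference is only 2 and 1 mmHg.

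**Conclusion.** The point holds as an optional improvement to a descriptive safety table. The planned pediatric mean change in blood pressure includes growth, and the plan has no means of separating it.

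On the protocol's charts the size is about +2.6 mmHg systolic in both sexes, and +2.5 (girls) or +3.5 (boys) diastolic, by Day 665. This rests on four assumptions: the middle height column, a cross-sectional 95th percentile standing in for a typical child's course over time, a child who keeps the same column and percentile, and equal weight on entry ages 2 to 10.

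These figures are not a forecast for the cohort. Its age mix is not given, the first five children must be 9 to 17, and no chart covers ages 13 to 17, so the actual drift is unknown. The plan breaks no commitment, and the primary endpoint and decision rules are untouched.

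**What to change.** Add two pediatric summaries to SAP 6.12.1.5 and state that both are descriptive and set no on-treatment stopping limit.

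1. **Chart-referenced pressure, measurements at ages 2 to 12.** By visit, present systolic and diastolic pressure, and their change, as the difference from the tabulated 95th percentile for current age, sex and most recent height. Use the nearest tabulated height column, and the end column for heights outside the range. Show change only where baseline and visit both fall at age 12 or under, with n per visit. Take heights from the visits in the protocol's schedules of activities, and note that SAP 4.2.5 lists fewer: it omits Cycles 5, 9, 13, 17, 21 and 24.

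2. **Reaching the age-specific limit.** Among pediatric participants below the Exclusion 12.5 limit at analysis baseline (SAP 4.2), give n (%) with a later systolic or diastolic pressure at or above the limit for current age. Give this for any visit and for two consecutive visits, split by age at measurement (12 and under; 13 and over). Judge each reading against the limit for age on that date. Footnote the jump at 13: in the middle column the systolic limit goes from 134 (girls) or 133 (boys) at age 12 to 140. Report separately those already at or above the limit at baseline.

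Adults need neither summary, since one fixed limit applies and growth is not an issue.

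The cost is a short SAP addition and modest programming. The measurements are already collected and the charts are in the protocol. There are three downsides. Any-visit counts over 16 scheduled post-baseline Treatment Phase visits will include one-off high readings. Consecutive visits are unevenly spaced: 4 weeks apart up to Cycle 7, mostly 8 weeks after that, and 16 weeks between long-term follow-up visits. Children leave the first summary at age 13.
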